11.2.2 Disease Parameters

Measurable disease. Measurable lesions are defined as those that can be accurately measured in at least one dimension (longest diameter to be recorded) as ≥ 10 mm with CT scan, MRI, or calipers by clinical exam. All tumor measurements must be recorded in millimeters (or decimal fractions of centimeters).

For multifocal intracranial disease, no more than 5 target measurable lesions (each ≥ 10 mm in diameter in both dimensions) should be selected for measurement. Target lesions should be selected on the basis of their size (lesions with longest diameter), be representative of other lesions and lend themselves to reproducible repeated measurements.

Non-measurable disease. Unidimensionally measurable lesions, masses with margins not clearly defined, lesions with maximal diameter < 1 cm.

11.2.3 Methods for Evaluation of Disease

All measurements should be taken and recorded in metric notation using a ruler, calipers, or a digital measurement tool. All baseline evaluations should be performed as closely as possible to the beginning of treatment and never more than 4 weeks before the beginning of the treatment.

The same method of assessment and the same technique should be used to characterize each identified and reported lesion at baseline and during follow-up. Imaging-based evaluation is preferred to evaluation by clinical examination unless the lesion(s) being followed cannot be imaged but are assessable by clinical exam.

Conventional head CT and brain MRI. This guideline has defined measurability of lesions on CT scan based on the assumption that CT thickness is 5 mm or less. If CT scans have slice thickness greater than 5 mm, the minimum size of a measurable lesion should be twice the slice thickness.

11.2.4 Response Criteria

11.2.4.1 Evaluation of Intracranial Lesions

Complete Response (CR): Requires all of the following:

- complete disappearance of all enhancing measurable and nonmeasurable disease sustained for at least 4 weeks
- no new lesions
- stable or decreasing corticosteroids (the steroid dose at the time of the scan evaluation should be no greater than the dose at time of baseline scan)
- stable or improved clinically

Participants with non-measurable disease cannot have a complete response. The best possible response is stable disease.

Partial Response (PR): All of the following criteria must be met:

- Greater than or equal to 50% decrease compared to baseline in the sum of products of perpendicular diameters of all measurable enhancing lesions sustained for at least 4 weeks. In the absence of a confirming scan 4 weeks later, this scan will be considered only stable disease.
- no progression of non-measurable disease.
- no new lesions
- stable or reduced corticosteroid dose (the steroid dose at the time of the scan evaluation should be no greater than the dose at time of baseline scan)
- stable or improved clinically

Progressive Disease (PD): At least one of the following must be true:

- $\geq 25\%$ increase in the sum of products of all measurable lesions over smallest sum observed (over baseline if no decrease) using the same techniques as baseline
- clear worsening of any nonmeasurable disease*
- appearance of any new enhancing lesion/site
- clear clinical worsening (unless clearly unrelated to this cancer, e.g. seizures, medication side effects, complications of therapy, cerebrovascular events, infection)
- failure to return for evaluation due to death or deteriorating condition

* Progression of non-measurable CNS lesions is defined as follows:

- a lesion initially at baseline $\leq 5\text{mm}$ in diameter that increases to $\geq 10\text{mm}$ in diameter, or
- a lesion initially at baseline 6-9 mm in diameter that increases by at least 5 mm in diameter.

Stable Disease (SD): All of the following criteria must be met:

- Does not qualify for CR, PR or progression
- All measurable and non-measurable sites must be assessed using the same techniques as baseline
- Stable clinically.

A summary of the response criteria is in the below:

	Complete Response	Partial Response	Stable Disease	Progressive Disease
T1-Gd+	None	$\geq 50\%$ decrease	$<50\%$ decrease- $<25\%$ increase	$\geq 25\%$ increase*
New Lesion	None	None	None	Present*

Corticosteroids	Stable or decrease	Stable or decrease	Stable or decrease	Stable or increasing
Clinical Status	Stable or improved	Stable or improved	Stable or improved	Decrease*
Requirement for Response	All	All	All	Any*
NA=not applicable				
#: Progression occurs when any of the criteria with * is present Increase in corticosteroids alone will not be taken into account in determining progression in the absence of persistent clinical deterioration				

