1.3 Secondary Objectives

1. To describe the toxicity of nivolumab and ipilimumab in brain and leptomeningeal metastases.
2. To estimate the central nervous system response rate (parenchymal brain metastases) of nivolumab and ipilimumab in patients with leptomeningeal disease
3. To estimate the systemic response rate of nivolumab and ipilimumab in patients with brain metastases
4. To estimate leptomeningeal disease response of nivolumab and ipilimumab in patients with leptomeningeal metastases.
5. To estimate the systemic progression free-survival of patients receiving nivolumab and ipilimumab.
6. To estimate the intracranial progression free-survival of patients receiving nivolumab and ipilimumab.

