11.1.2 Disease Parameters

Measurable disease. Measurable lesions are defined as those that can be accurately measured in at least one dimension (longest diameter to be recorded) as ≥ 20 mm by chest x-ray or ≥ 10 mm with CT scan, MRI, or calipers by clinical exam. All tumor measurements must be recorded in millimeters (or decimal fractions of centimeters).

Note: Tumor lesions that are situated in a previously irradiated area might or might not be considered measurable.

Malignant lymph nodes. To be considered pathologically enlarged and measurable, a lymph node must be ≥ 15 mm in short axis when assessed by CT scan (CT scan slice thickness recommended to be no greater than 5 mm). At baseline and in follow-up, only the short axis will be measured and followed.

Non-measurable disease. All other lesions (or sites of disease), including small lesions (longest diameter <10 mm or pathological lymph nodes with ≥ 10 to <15 mm short axis), are considered non-measurable disease. Bone lesions, leptomeningeal disease, ascites, pleural/pericardial effusions, lymphangitis cutis/pulmonitis, inflammatory breast disease, abdominal masses (not followed by CT or MRI), and cystic lesions are all considered non-measurable.

Note: Cystic lesions that meet the criteria for radiographically defined simple cysts should not be considered as malignant lesions (neither measurable nor non-measurable) since they are, by definition, simple cysts.

‘Cystic lesions’ thought to represent cystic metastases can be considered as measurable lesions, if they meet the definition of measurability described above. However, if non-cystic lesions are present in the same participant, these are preferred for selection as target lesions.

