11.2.1 Definitions

Evaluable for objective response. Only those participants who have measurable CNS disease present at baseline, have received at least one cycle of therapy, and have had their disease re-evaluated will be considered evaluable for target disease response in the CNS. These participants will have their response classified according to the definitions stated below. (Note: Participants who exhibit objective disease progression prior to the end of cycle 1 will also be considered evaluable.)

Evaluable non-measurable evaluable disease. Participants who have lesions present at baseline that are evaluable but do not meet the definitions of measurable disease, have received at least one cycle of therapy, and have had their disease re-evaluated will be considered evaluable for non-target disease. The response assessment is based on the presence, absence, or unequivocal progression of the lesions.

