11.2.4.2 Evaluation of Best Overall Response

The best overall response is the best response recorded from the start of the treatment until disease progression/recurrence (taking as reference for progressive disease the smallest measurements recorded since the treatment started). The patient's best response assignment will depend on the achievement of both measurement and confirmation criteria. If a response recorded at one scheduled MRI does not persist at the next regular scheduled MRI, the response will still be recorded based on the prior scan, but will be designated as a non-sustained response. If the response is sustained, i.e. still present on the subsequent MRI at least four weeks later, it will be recorded as a sustained response, lasting until the time of tumor progression. Participants without measurable disease may only achieve SD or PD as their best “response.”

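### Section 11.2.4.1 omits the word 'only': as worded it bars an intracranial response for anyone with both measurable and non-measurable disease, against the criteria around it

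*Combined protocol and SAP*

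**What the plan says.** Endpoint. Objective 2 in Section 1.3 opens "To estimate the central nervous system response rate (parenchymal brain metastases". Section 13.6 analyses it as the proportion of patients with CR or PR by RANO in intraparenchymal metastases, with a two-sided 90% exact binomial interval.

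The intracranial rules are spread over four places:

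- Section 11.2.1, who is evaluable for objective response: "Only those participants who have measurable CNS disease present at baseline", with at least one cycle received and disease re-evaluated. A second group has only lesions that do not meet the definition of measurable disease.
- Section 11.2.2, non-measurable disease: "Unidimensionally measurable lesions, masses with margins not clearly defined, lesions with maximal diameter < 1 cm".
- Section 11.2.4.1. CR requires, among other things, "complete disappearance of all enhancing measurable and nonmeasurable disease sustained for at least 4 weeks". PR requires a decrease of at least 50% in the sum of products of the measurable enhancing lesions, sustained for at least 4 weeks, and, among other things, "no progression of non-measurable disease". Between the two stands the sentence at issue: "Participants with non-measurable disease cannot have a complete response. The best possible response is stable disease".
- Section 11.2.4.2: "Participants without measurable disease may only achieve SD or PD as their best" response.

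Leptomeningeal disease is an entry requirement (Section 3.1). It is named as non-measurable in the extracranial RECIST section, 11.1.2 ("Bone lesions, leptomeningeal disease, ascites, pleural/pericardial effusions, lymphangitis cutis/pulmonitis"), and in the irRC appendix. The intracranial definition in Section 11.2.2 does not name it. Leptomeningeal response has its own table in Section 11.4.

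**The concern.** Participants *with* non-measurable disease and participants *without* measurable disease are different groups. Those who have both kinds of disease belong to the first and not to the second. Section 11.2.4.1 caps them at stable disease; Section 11.2.4.2 does not.

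A central reader who applies the sentence in Section 11.2.4.1 literally will record SD where the PR criteria are met. The error runs one way: it can turn responders into non-responders but never the reverse. It would lower the intracranial response rate and remove those participants from the duration of response in Section 11.2.4.3. Section 11.3 adds to the risk, because it sends central review to RANO criteria in a Section 12.1.4. Section 12.1 is Data Reporting and has no such subsection.

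**Working it through.** **The plan's own figure.** The only number attached to this endpoint is the maximum interval width of 0.42 for 18 patients (Section 13.6). The exact (Clopper-Pearson) 90% limits for x responders among n are the 0.05 quantile of Beta(x, n − x + 1) and the 0.95 quantile of Beta(x + 1, n − x). For n = 18 the width is greatest at x = 9 and equals 0.4176, which rounds to 0.42. The figure reproduces, and the rewording does not change it. The question is one of definition.

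**One scan, two classifications.** Take a hypothetical participant with one metastasis of 15 mm × 15 mm and one lesion of 6 mm at baseline. At follow-up, confirmed at least 4 weeks later, the first measures 10 mm × 10 mm and the second is unchanged. There are no new lesions, steroids are not increased and the participant is clinically stable.

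1. Section 11.2.2: the first lesion is measurable (at least 10 mm in both dimensions). The second is non-measurable (under 1 cm).
2. Section 11.2.1: measurable CNS disease is present, so the participant is evaluable for objective response.
3. PR criteria, Section 11.2.4.1: the product falls from 15 × 15 = 225 mm² to 10 × 10 = 100 mm², a decrease of 125/225 = 55.6%, which is at least 50%. Non-measurable disease has not progressed. Result: **PR**.
4. Section 11.2.4.2: the participant has measurable disease, so the cap does not apply. Result: **PR**.
5. The sentence in Section 11.2.4.1, read literally: the participant has non-measurable disease. Result: **SD**.

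This uses only the definitions of Section 11.2; no classification of leptomeningeal disease is needed.

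**Internal consistency of Section 11.2.4.1.** If non-measurable disease barred CR and PR, the CR criterion would have no reason to require such disease to disappear, and the PR criterion no reason to require that it not progress. Both criteria presuppose responders who also have non-measurable disease.

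**Size.** If k of n evaluable participants meet PR or CR and also have non-measurable disease, the literal reading lowers the response rate by k/n. The documents give neither k nor n; n is the number with measurable CNS disease, which eligibility does not require. Per reclassified responder (k = 1), over an assumed range of n:

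| n (assumed) | fall in response rate, 1/n |
|---|---|
| 18 | 0.056 |
| 10 | 0.100 |
| 6 | 0.167 |
| 4 | 0.250 |

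**Leptomeningeal enhancement.** Suppose every parenchymal lesion disappears while stable leptomeningeal enhancement remains, and that enhancement is counted as non-measurable disease. CR fails, because not all enhancing disease is gone. PR is met: measurable disease has fallen by 100% and non-measurable disease has not progressed. The participant still counts in the combined CR-or-PR proportion, so only the label changes.

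**The case against.** The strongest reply is that the intended rule is not in doubt. Section 11.2.1 separates participants with measurable CNS disease from those whose lesions are all non-measurable, and the sentence in Section 11.2.4.1 most naturally refers to the second group. Section 11.2.4.2 states the cap in those terms, and the CR and PR criteria make sense only on that reading. The endpoint is secondary, descriptive and tested against nothing. All of this stands, and it is why the point is minor. It does not make the sentence correct: as worded it gives a different answer from the text around it, and response is assigned from the written criteria.

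A reader might go further and infer that nobody can have an intracranial response, since every participant has leptomeningeal disease and leptomeningeal disease is non-measurable. The result would then be fixed at 0/18, with an upper 90% limit of 1 − 0.05^(1/18) = 0.153. The documents do not support this, for three reasons. The non-measurable label for leptomeningeal disease comes from the RECIST section and the irRC appendix, not from Section 11.2.2. Entry can rest on cytology or biopsy without an imaging lesion. And 18 is not the denominator, because Section 11.2.1 limits it to participants with measurable CNS disease.

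A reader might also infer that persistent leptomeningeal enhancement removes parenchymal responders from the analysis. When the enhancement is stable it does not, as the last step of the check shows.

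**Conclusion.** The concern holds as a wording defect of minor severity. The sentence in Section 11.2.4.1 contradicts the CR and PR criteria beside it, Section 11.2.1 and Section 11.2.4.2 for participants who have both measurable and non-measurable intracranial disease. For them the same scan can be PR or SD, and secondary endpoint 2 can be understated by k/n. The size is unknown because the documents give neither number; the values of n in the check are assumptions.

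The surrounding text shows that participants with measurable CNS disease are meant to be able to respond, so a response rate of zero is not the expected result. Survival at 3 months, the two-stage rule and the primary analysis are unaffected.

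**What to change.** In Section 11.2.4.1, begin the sentence *Participants with only non-measurable disease*, so that it agrees with Section 11.2.4.2.

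As a clarification, state in Section 11.2.4 that leptomeningeal enhancement is scored under Section 11.4 and does not count as non-measurable disease for parenchymal CR or PR. Limit that statement to response. Whether leptomeningeal worsening counts as intracranial progression is a separate matter and should not be settled by implication.

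Correct the cross-reference in Section 11.3 at the same time, and notify the imaging core, if possible before responses are read. The cost is one inserted word, one added sentence, a corrected section number and a note. No new data are needed, and no stated sample size or interval width changes.

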11. MEASUREMENT OF EFFECT

Response in the CNS and response in non-CNS sites will be evaluated and recorded separately in this trial.

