13.1 Study Design/Endpoints

Primary endpoint: Rate of overall survival at 3 months

Secondary Endpoints:

1. Toxicity by CTCAE criteria (grade 3 or higher hematologic toxicity; grade 3 or higher neurologic toxicity)
2. Intracranial response in patients with leptomeningeal metastases
3. Extracranial response as determined by RECIST and irRC
4. Leptomeningeal disease response as defined in section 11.4
5. Time to the first occurrence of extracranial disease progression, or death from any cause
6. Time to the first occurrence of intracranial disease progression, or death from any cause

Exploratory Endpoints: Genetic alterations

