Extracranial PFS and Intracranial PFS: Extracranial PFS (EPFS) is defined as the time from first dose of study drug to documented extracranial progression (per RECIST or irRC) or death, whichever occurs first. Intracranial PFS (IPFS) is defined as the time from first dose of ipilimumab and nivolumab to documented intracranial progression (RANO) or death, whichever occurs first. For both endpoints, the follow-up of patients who have neither died nor progressed at the time of analysis will be censored at the date of last adequate disease assessment. Each cohort will be presented separately. Median EPFS and IPFS will be presented and accompanied by 90% confidence intervals estimated using log(-log(survival)) methodology. Point estimates at 3 and 6 months will also be presented with confidence intervals.

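### The intracranial progression rule counts clinical decline from extracranial disease as progression in the brain, which mislabels the site of failure and shortens intracranial PFS by a probably modest amount

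*Combined protocol and SAP*

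**What the plan says.** Section 11 opens with a principle: "Response in the CNS and response in non-CNS sites will be evaluated and recorded separately in this trial".

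For the brain, Section 11.2.4.1 sets the threshold as "Progressive Disease (PD): At least one of the following must be true". Two of the five items are clinical. The first covers a decline seen by the investigator: "clear clinical worsening (unless clearly unrelated to this cancer, e.g. seizures, medication side effects, complications of therapy, cerebrovascular events, infection"). The second covers patients who are not seen again, and no exception is attached to it: "failure to return for evaluation due to death or deteriorating condition".

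The summary table repeats the rule. A decrease in clinical status carries an asterisk, and the note says "Progression occurs when any of the criteria with * is present". Neither place requires an imaging change to accompany the decline.

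For CR and PR the same section also requires the patient to be "stable or improved clinically". SD needs a stable clinical status. None of these conditions is limited to neurologic status.

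Secondary endpoint 6 in Section 13.1 is "Time to the first occurrence of intracranial disease progression, or death from any cause". Section 13.6 takes the event straight from the response rule: "documented intracranial progression (RANO) or death, whichever occurs first". Section 3.1.1 admits any solid tumor.

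**The concern.** The exception turns on whether the decline is related to the cancer, not on whether it comes from the CNS. That would be enough if the cancer were confined to the brain. Here the cancer is a metastatic solid tumor, and its growth in the liver, lung or bone is plainly related to it. The listed exceptions are all non-progression causes, and extracranial progression is not among them. The failure-to-return item carries no exception at all.

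A patient who declines from systemic disease with an unchanged brain MRI therefore has an intracranial event. At stake are two secondary results that the plan reports by site: IPFS, and the intracranial response rate, for which a systemic decline can make the clinical condition fail.

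**Working it through.** **1. The plan's own figure.** The stated number tied to an affected endpoint is the maximum width, 0.42, of the 90% exact interval for intracranial response with 18 patients (Section 13.6). The Clopper-Pearson interval is widest at 9 of 18, from 0.291 to 0.709, a width of 0.418. The figure reproduces. It does not depend on how progression is defined.

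**2. The same patient under each rule.** Suppose a patient declines generally from suspected visceral progression, before any body scan shows it, with a stable brain MRI and no new neurologic symptoms.

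| Rule | Result |
|---|---|
| Intracranial, 11.2.4.1 and its table | Progression, on clinical worsening alone |
| Extracranial, 11.1.4.4 | Symptomatic deterioration if treatment has to stop; not progression without objective evidence |
| Leptomeningeal, neurologic column, 11.4 | Not progression; new neurologic symptoms due to neoplastic meningitis are needed |

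The patient counts as failing in the brain and not, so far, outside it, which is the reverse of the clinical picture. Section 11.2.5 is also unrestricted: after an initial radiographic progression, any significant decline confirms it and the date is set back.

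**3. Size for IPFS (illustration).** The documents give no rate of decline from extracranial disease, so this step rests on assumptions.

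- Median survival *m*: 2, 3 or 4 months (the 2 to 4 month range is in Section 13.2).
- Median time to true intracranial progression *i*: 4 or 6 months (assumed).
- Share *f* with an extracranial decline before death: 10%, 25% or 50% (assumed).
- Lead time *L* from decline to death: 2, 4 or 6 weeks (assumed), divided by 4.345 to give months. If death comes sooner than *L*, the decline is placed at time zero.
- Death and intracranial progression are independent and exponential.

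With decline not counted, IPFS at *t* months is S(t) = 2^(−t(1/m + 1/i)). With decline counted, a patient in the share *f* must survive past *t* + *L*, so

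- fall in IPFS at *t* = S(t) × f × (1 − 2^(−L/m));
- share of patients whose decline is scored ahead of any true event = f × [1 − 2^(−L/m) × m/(m + i)].

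Extremes over the grid:

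- Largest 3-month fall (m = 3, i = 6, f = 0.5, L = 6 weeks): S(3) = 2^(−1.5) = 0.354; 0.354 × 0.5 × (1 − 0.727) = 0.048.
- Smallest 3-month fall (m = 4, i = 4, f = 0.1, L = 2 weeks): 0.354 × 0.1 × (1 − 0.923) = 0.003.
- Largest 6-month fall (m = 4, i = 6, f = 0.5, L = 6 weeks): S(6) = 2^(−2.5) = 0.177; 0.177 × 0.5 × (1 − 0.787) = 0.019.
- Smallest mislabelled share (m = 4, i = 4, f = 0.1, L = 2 weeks): 0.1 × (1 − 0.923 × 0.5) = 0.054, or 18 × 0.054 ≈ 1 patient.
- Largest mislabelled share (m = 2, i = 6, f = 0.5, L = 6 weeks): 0.5 × (1 − 0.620 × 0.25) = 0.42, or 18 × 0.42 ≈ 8 patients.

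Simulating the same model (1,000,000 draws per setting) puts the fall in median IPFS at 0.02 to 0.46 months.

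**4. Response.** Section 11.2.4.1 treats a PR without a confirming scan 4 weeks later as stable disease. Section 11.2.4.2 counts the best response up to progression and keeps one that fails to persist at the next MRI as non-sustained. So a systemic decline can cost a response if it comes before or at the response scan, or before confirmation. A response already recorded need not be lost. Each lost responder is 1/18 = 5.6 points if all 18 are in the denominator, and more if fewer have measurable CNS disease.

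**The case against.** The best defence is context. The item stands under the heading for intracranial lesions, and two of its exceptions, seizures and cerebrovascular events, are rival explanations for neurologic change. Section 13.6 asks for documented progression, Section 11.2.3 prefers imaging to clinical examination, and Section 11.3 sends every brain MRI to central review. Many investigators would read the item as neurologic. That makes the literal outcome less than certain in practice, but it does not close the gap: no sentence limits the item, central review covers scans only, and nobody is named to attribute a clinical decline.

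The objections on size stand. A reader might multiply 5.6 points per patient by, say, 3 to 6 patients and infer a 17 to 33 point loss in IPFS. The documents do not support that as the expected effect. Death from any cause is already an event and survival is short, so a decline moves a landmark estimate only if it falls before the landmark and the patient is still alive and free of true intracranial progression at it. All 3 to 6 patients would have to meet that condition at the same landmark.

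It is also fair that the present rule errs toward earlier events, and that attribution in patients with disease at both kinds of site is partly subjective.

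**Conclusion.** The point holds. As written, the rule scores decline from extracranial disease as an intracranial event, against the separation promised in Section 11 and out of step with Sections 11.1.4.4 and 11.4. The chief consequence is a wrong site of failure. The shift in IPFS is probably modest: 0.3 to 4.8 points at 3 months in the illustration, with the direction (shorter IPFS) certain and the amount dependent on the assumed shares, lead times and exponential model.

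Two stronger readings go too far. One is that any systemic decline cancels an intracranial response; Section 11.2.4.2 can preserve one already recorded. The other is that the trial's main conclusion is at risk. The primary endpoint is survival at 3 months, and the sample size, error rates and interval widths do not change. The plan should be amended, but as a repair to secondary endpoints.

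**What to change.** Amend the definition used for intracranial response and IPFS only:

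1. Limit the clinical item in CR, PR, SD and PD, and the deterioration part of failure to return, to neurologic worsening attributed to CNS disease. Death is already an IPFS event.
2. Name who attributes the cause and record it in one cause-of-decline field. The calendar in Section 10 already requires a neurologic assessment at each physical examination, so no visit or test is added.
3. State how decline from extracranial disease without objective progression is handled in both IPFS and extracranial PFS, consistently with Section 11.1.4.4. Otherwise it may be an event under neither until imaging or death.
4. Report a sensitivity analysis of IPFS and intracranial response under the present wording.
5. Reconcile the opening of Section 11 with Sections 11.1.4.4, 11.2.4.1 and its table, 11.2.5, 11.4 and 13.6.

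Progression also ends therapy under Sections 5.5 and 11.2.5. The amendment should say that it governs endpoint scoring and leaves the rules for stopping treatment unchanged.

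The cost is wording and one data field. The downside is some subjectivity in attribution and a definition that can only lengthen IPFS in a single-arm trial, which is why the sensitivity analysis should accompany it.
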